## **Exclusion Criteria**

1. Pregnancy or Breast-Feeding: Pregnant or breast-feeding women will not be entered on this study due to risks of fetal and teratogenic adverse events as seen in animal/human studies. Pregnancy tests must be obtained in girls who are post-menarchal. Males or females of reproductive potential may not participate unless they have agreed to use two methods of birth control- a medically accepted barrier method of contraceptive method (e.g., male or female condom) and a second effective method of birth control- during protocol therapy and for at least 4 months after the last dose of cabozantinib. Abstinence is an acceptable method of birth control.
2. Concomitant Medications:
  - a. Corticosteroids: Patients receiving corticosteroids who have not been on a stable or decreasing dose of corticosteroid for at least 7 days prior to enrollment are not eligible.
  - b. Investigational drugs: Patients who are currently receiving another investigational drug are not eligible.
  - c. Anti-cancer agents: patients who are currently receiving other anti-cancer agents are not eligible.
  - d. CYP3A4 active agents: Patients must not be receiving any of the following potent CYP3A4 inducers or inhibitors: erythromycin, clarithromycin, ketoconazole, azithromycin, itraconazole, grapefruit juice or St. John's wort. A list of other known CYP3A4 inducers and inhibitors that should be discontinued prior to initiation of protocol therapy and should be avoided during study therapy if reasonable alternatives exist is included in Appendix V.
  - e. Patients who are receiving systemic therapeutic treatment anticoagulation are not eligible. Patients receiving prophylactic systemic anticoagulation will be allowed with heparin or LMWH as long as eligibility PT/INR requirements are met. Concomitant anticoagulation with oral anticoagulations (e.g. warfarin, direct thrombin and Factor Xa inhibitors) or platelet inhibitors (eg. Clopidogrel) are not allowed.
  - f. Enzyme-inducing anticonvulsants: Patients must not have received enzyme-inducing anticonvulsants within 14 days prior to enrollment (See Appendix III for a list of unacceptable enzyme inducing anticonvulsants).
  - g. QTc Agents: Patients who are receiving drugs that prolong QTc are not eligible (See Appendix IV for a list of agents).
3. Patients must be able to swallow intact tablets. Patients who cannot swallow intact tablets are not eligible.

4. Patients with active bleeding are not eligible. Specifically, no clinically significant GI bleeding, GI perforation, intra-abdominal abscess or fistula for 6 months prior to enrollment, no hemoptysis or other signs of pulmonary hemorrhage for 3 months prior to enrollment.
5. Patients with evidence of an acute intracranial or intratumoral hemorrhage on CT or MRI are not eligible (patients with evidence of resolving hemorrhage will be eligible).
6. Major surgery within 28 days of enrollment. Complete wound healing from major or minor surgery must have occurred prior to enrollment. Minor surgery (including uncomplicated tooth extractions) within 7 days of enrollment. Subjects with clinically relevant ongoing complications from prior surgery are not eligible.
7. Concurrent uncontrolled hypertension defined as sustained blood pressure > 95th percentile for age, height and gender (systolic or diastolic) despite optimal antihypertensive treatment within 7 days of the first dose of study treatment.
8. Patients with any medical or surgical conditions that would interfere with gastrointestinal absorption of this oral agent are not eligible.
9. Infection: Patients who have an uncontrolled infection are not eligible.
10. Patients who have received a prior solid organ transplantation are not eligible.
11. Patients who in the opinion of the investigator may not be able to comply with the safety monitoring requirements of the study are not eligible.
12. Subjects who have received cabozantinib or have an allergy to cabozantinib are excluded. Subjects who have previously received tyrosine kinase inhibitors are allowed.
13. Subjects who have not received radiation therapy as part of their prior treatment are excluded.

## 6. Enrollment/ Study population

Eleven patients between the ages of 2 years and 21 years with a diagnosis of recurrent or refractory central nervous system tumor.

All patients will be enrolled through the Neuro-Oncology Program at Riley Hospital for Children at IU Health. This is an open label trial and there will be no randomization.

**Justification for Institutional Enrollment:** Between 2014 to date (5/2016), 15 patients with newly diagnosed high grade glioma were evaluated in the Neuro-oncology clinic at Riley Hospital for Children. As of 5/2016, 14 of 15 have recurred, relapsed, or died as a consequence of their disease. Based on this we expect to be able to enroll 11 subjects on this study as proposed within the 5 year period of enrollment.

## 7. Study Procedures

**Pre-study evaluations:** The investigational nature and objectives of the trial, the procedures and treatments involved and their attendant risks and discomforts and potential alternative therapies will be carefully explained to the patient and or the patient's parent(s) or guardian if the patient is a child, and a signed informed consent and assent will be obtained according to institutional and federal guidelines.

Diagnostic or laboratory studies performed exclusively to determine eligibility for this trial must only be done after obtaining written informed consent. Documentation of the informed consent for screening will be maintained in the subject's research chart. Studies or procedures that were performed for clinical indications (not exclusively to determine eligibility) may be used for baseline values even if the studies were done before informed consent was obtained.

Within 14 days of starting study drug, pre-study evaluations include: History and physical exam, laboratory studies, performance status, pregnancy test (for females of child bearing age), 12-lead ECG and MRI of brain +/- spinal cord.

**Criteria for Starting Subsequent cycles:** A cycle may be repeated every 28 days(+/- 3 days) if the subject does not have evidence of progressive disease and has again met laboratory parameters as defined in the eligibility criteria, with the exception of ANC, which must be  $\geq 1000/\text{mm}^3$  to start each cycle.

History and physical exam, laboratory studies, performance status, study drug and corticosteroid drug diaries will be collected every 15 days (+/- 72 hours) after initiation of drug for cycles 1-3.

History and physical exam, laboratory studies, performance status, study drug and corticosteroid drug diaries will be collected every 28 days (+/- 72 hours) for cycles 4-12.

MRI's will be performed every 3 months (+/- 1 week).

12-lead ECG will be performed at pre-study, End of Cycle 1, End of Cycle 3 and End of Cycle 6, unless additional ECGs are required per protocol guidance (dose modification or concomitant medication usage)

Study Schedule: STUDIES TO BE OBTAINED	Pre-Study 	Cycle 1 ^	Cycle 2, 3 ^	Cycle 4-12 ^	Completion of Study
Informed Consent obtained	X				
History (including Con Meds)	X	Day 28	Days 15, 28	Day 28	X
Physical exam with vital signs and pulse ox	X	Days 15 and 28	Days 15, 28	Day 28	X
Height, weight, BSA	X	Day 28	Days 15, 28	Day 28	X
Blood pressure 	X	Days 15 and 28	Days 15, 28	Day 28	X
Performance Status	X	Day 28	Days 15, 28	Day 28	X
Subject Diaries (Study drug and steroid use)	X	Day 15 & 28	Day 15 & 28)	Day 28	X
CBC, differential, platelets	X	Days 15 and 28	Days 15, 28	Day 28	X
CMP  with Ca, Mg, Phos, lipase, amylase	X	Days 15 and 28	Days 15, 28	Day 28	X
PT, PTT, INR	X	Day 28	Day 28	Day 28	X
Urinalysis	X	Day 28	Day 28	Day 28	X
Urine protein/creatinine	X	Day 28	Day 28	Day 28	X
Pregnancy test 	X 		Day 28 Cycle 2	Day 28 Cycles 4, 6, 8, 10, 12	X
Thyroid stimulating hormone	X	Day 28	Day 28 Cycle 3	Day 28 Cycles 6, 9, 12	X
12- lead ECG 	X	Day 28	Day 28 Cycle 3	Day 28 Cycles 6	
MRI of brain +/- spinal cord if clinically indicated 	X		Day 28 Cycle 3	Day 28 Cycles 6 and 9	X
Assess for adverse events		x	x	x	x

^ Studies may be obtained within +/- 72 hours unless otherwise specified within the table

1. All studies to determine eligibility must be performed within 2 weeks prior to enrollment. Consent must be obtained prior to enrollment but does not expire at 2 weeks.

2. Baseline BP should be obtained by collecting 3 serial BP measurements at least 5 minutes apart and then averaging the second and third BP measurements.

3. CMP should include: sodium, potassium, chloride, bicarbonate, blood urea nitrogen, creatinine, glucose, albumin, total protein, SGOT (AST), SGPT (ALT), total bilirubin, alkaline phosphatase

4. For females of childbearing age

5. If the subject starts a medication with substantial evidence that the drug prolongs the QT interval, then ECG monitoring must be performed at the end of each cycle while on the medication

6. For subjects with Complete or Partial response confirmatory MRI per RANO criteria will be performed within 6 weeks. For scheduling purpose, obtain within +/- 1 week of required observation

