#### 4.2 Dose, Schedule and Route

Study medication will be taken daily at a dose of 40 mg/m^2. Drug cycles will last 28 days and be continuous for up to 12 months of therapy on study.

Cabozantinib will be held for subjects who experience toxicity until the toxicity has decreased to grade 1. Cabozantinib will then be reduced by one dose level and not re-escalated in subsequent cycles. Subjects who experience toxicity at dose level -1 will be off study (See Section 7.0 for Dose Modification guidelines).

Dose Level	Dose (mg/m  /dose with max dose 60 mg/day)
-1	30 mg/m 
1	40 mg/m 

Actual dosing will be based on dosing nomogram in Appendix VI

Cabozantinib must be taken on an empty stomach. Subjects must be instructed not to eat for at least 2 hours before and at least 1 hour after taking cabozantinib. Subjects should be instructed to take their cabozantinib dose at approximately the same time every day. If a subject misses a dose, the dose may be taken later only if it is within 12 hours of when the missed dose should have been taken. The missed dose should not be made up if it is within 12 hours of the next scheduled dose.

Cabozantinib tablets should be swallowed whole with at least 8 ounces of water. The tablets should not be crushed. Grapefruit, grapefruit juice, Seville oranges and their products should be avoided by subjects taking cabozantinib.

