  - i. Platelet count  $\geq 100,000/\text{mm}^3$  (transfusion independent, defined as not receiving platelet transfusions for at least 7 days prior to enrollment)
  - ii. Patients with bone marrow metastatic disease will not be eligible.
- b. Adequate renal function defined as:
  - i. Creatinine clearance or radioisotope GFR  $\geq 70\text{mL}/\text{min}/1.73\text{ m}^2$  **or** a serum creatinine based on age/gender as follows:

Age	Maximum Serum	
	Male	Female
2 to < 6 years	0.8	0.8
6 to < 10 years	1	1
10 to < 13 years	1.2	1.2
13 to < 16 years	1.5	1.4
$\geq 16$ years	1.7	1.4

The threshold creatinine values in this table were derived from the Schwartz formula for estimating GFR (Schwartz et al. J. Peds, 106:522, 1985) utilizing child length and stature data published by the CDC.

- ii. Urine protein:  $\leq 30\text{ mg}/\text{dL}$  in urinalysis or  $\leq 1+$  on dipstick, unless quantitative protein is  $< 1000\text{ mg}$  in a 24 hour urine sample.
- c. Adequate Liver Function Defined as:

- i. Bilirubin (sum of conjugated + unconjugated)  $\leq 1.5 \times$  upper limit of normal (ULN) for age
    - ii. SGPT (ALT)  $\leq 110$  U/L. For the purpose of this study, the ULN for SGPT is 45 U/L.
    - iii. Serum albumin  $\geq 2.8$  g/dL.
  - d. Adequate coagulation status defined as: PT and INR  $\leq 1.5 \times$  ULN
  - e. Adequate pancreatic function defined as: Serum amylase and lipase  $\leq 1.5 \times$  ULN
  - f. Adequate blood pressure control defined as: A blood pressure (BP)  $\leq$  the 95th percentile for age, height and gender (Appendix II) despite optimal antihypertensive treatment within 7 days of the first dose of the study treatment. Please note that 3 serial blood pressures should be obtained and averaged to determine baseline BP.
  - g. Central nervous system function defined as: Patients with seizure disorder may be enrolled if receiving non-enzyme inducing anticonvulsants and well controlled. See Appendix III for a list of recommended non-enzyme inducing anticonvulsants.
  - h. Adequate cardiac function defined as:
    - i. No history of congenital QTc syndrome, NYHA Class III or IV congestive heart failure (CHF)
    - ii. No clinical significant cardiac arrhythmias, stroke or myocardial infarction within 6 months prior to enrollment
    - iii. QTc  

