## 7.1 Dose Modifications

### Dose Modifications of Cabozantinib for Treatment-Related AEs

CTCAE v.5.0 Grade	Recommended Guidelines for Management a
Grade 1 AEs	Add supportive care as indicated. Continue cabozantinib treatment at the current dose level if AE is manageable and tolerable.
Grade 2 AEs which are tolerable and are easily managed	Continue cabozantinib treatment at the current dose level with supportive care.
Grade 2 AEs which are intolerable and cannot be adequately managed	At the discretion of the investigator, cabozantinib should be dose reduced or interrupted.  Note: It is recommended that dose holds be as brief as possible.
Grade 3 AEs (except clinically non-relevant laboratory abnormalities)	Cabozantinib should be interrupted unless the toxicity can be easily managed with a dose reduction and optimal medical care.  Note: It is recommended that dose holds be as brief as possible.
Grade 4 AEs (except clinically non-relevant laboratory abnormalities)	Subjects should have cabozantinib interrupted immediately. Discontinue cabozantinib unless the following criteria are met: 
 
• Subject is deriving clear clinical benefit as determined by the investigator and agreed by the Sponsor
 
• Toxicity can be managed with a dose reduction following recovery to Grade 1 (or baseline) and optimal medical care
 

AE, adverse event.

Note: The dose delay and modification criteria for specific medical conditions are provided below.

a Study treatment dose adjustment is only needed if the toxicity was deemed related to cabozantinib treatment or had an unclear relationship to cabozantinib treatment.

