**Dose Modifications for Hematologic toxicity**

If a patient experiences dose-limiting Grade 4 neutropenia or thrombocytopenia, the treatment will be withheld. Counts should be checked every 3 - 4 days for thrombocytopenia and every other day for neutropenia during this time. If the toxicity resolves to meet eligibility parameters within 14 days of drug interruption, the patient may resume treatment at the next lower dose level. Doses reduced for toxicity will not be re-escalated, even if there is minimal or no toxicity with the reduced dose.

If dose-limiting toxicity does not resolve to meet eligibility or baseline parameters within 14 days of drug interruption, the patient must be removed from protocol therapy.

One dose reduction will be allowed for toxicity. If a patient does not tolerate reduced dose, they must be removed from protocol therapy.

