## Management of Treatment-emergent Proteinuria

[figure not shown]
Severity of Proteinuria (UPCR)	Management of Proteinuria
$\leq 1$ mg/mg ( $\leq 113.1$ mg/mmol)	
 
No change in cabozantinib treatment or monitoring
 

$> 1$ and $< 3.5$ mg/mg ( $> 113.1$ and $< 395.9$ mg/mmol)	
 
Consider confirming with a 24-hour protein assessment within 7 days
 
No change in cabozantinib treatment required if UPCR <math>\leq 2</math> mg/mg or urine protein <math>\leq 2</math> g/24 hours on 24-hour urine collection.
 
Dose reduce or interrupt cabozantinib treatment if UPCR <math>> 2</math> mg/mg on repeat UPCR testing or urine protein <math>> 2</math> g/24 hours on 24-hour urine collection. Continue cabozantinib on a reduced dose if UPCR decreases to <math>< 2</math> mg/mg. Consider holding cabozantinib treatment if UPCR remains <math>> 2</math> mg/mg despite a dose reduction until UPCR decreases to <math>< 2</math> mg/mg. Restart cabozantinib treatment at a reduced dose after a dose hold unless otherwise approved by sponsor.
 
Repeat UPCR within 7 days and once per week. If UPCR <math>< 1</math> mg/mg on 2 consecutive readings, UPCR monitoring can revert to protocol-specific times. (Second reading is confirmatory and can be done within 1 week of first reading.) If UPCR remains <math>> 1</math> mg/mg and <math>< 2</math> mg/mg for 1 month or is determined to be stable (<math>< 20\%</math> change) for 1 month, check urine protein/creatinine per protocol or as clinically indicated.
 

$\geq 3.5$ mg/mg ( $\geq 395.9$ mg/mmol)	
 
Hold cabozantinib treatment pending repeat UPCR within 7 days and/or 24-hour urine protein.
 
If <math>\geq 3.5</math> mg/mg on repeat UPCR, continue to hold cabozantinib treatment and check UPCR every 7 days. If UPCR decreases to <math>< 2</math> mg/mg, restart cabozantinib treatment at a reduced dose and monitoring of urine protein/creatinine should continue weekly until the UPCR decreases to <math>< 1</math> mg/mg. If UPCR remains <math>> 1</math> mg/mg and <math>< 2</math> mg/mg for 1 month or is determined to be stable (<math>< 20\%</math> change) for 1 month, check urine protein/creatinine per protocol or as clinically indicated.
 

Nephrotic syndrome	
 
Discontinue all study treatment
 

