### **Dose Modifications for Pancreatic Toxicity**

Cabozantinib should be held if patient experiences Grade 3 asymptomatic amylase or lipase elevation. Elevated laboratory parameters should be checked at least twice weekly until  $\leq$  Grade 1.

If lab values do not resolve to  $\leq 1$  Grade within 7 days of interruption or if toxicity recurs with re-challenge at reduced dose, then this will be considered dose-limiting. Cabozantinib will then be discontinued.

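### The cycle-start rule re-imposes the eligibility laboratory limits, Section 7.1 lets treatment continue outside them, and no section says which governs

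*Combined protocol and SAP*

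**What the plan says.** **Cycle start.** Section 7 (Criteria for Starting Subsequent cycles) allows a cycle to be repeated every 28 days, within 3 days either way, if there is no progression and the subject "has again met laboratory parameters as defined in the eligibility criteria". One carve-out follows, "with the exception of ANC, which must be" at least 1000/mm3. Inclusion criterion 8a already sets that same ANC value.

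**Eligibility limits brought in by that rule (inclusion criterion 8).** These include platelets of at least 100,000/mm3, ALT of at most 110 U/L with the ULN fixed at 45 U/L, and bilirubin of at most 1.5 x ULN. Criterion 8e, "Adequate pancreatic function defined as: Serum amylase and lipase", also sets 1.5 x ULN. Urine protein may be at most 30 mg/dL on urinalysis or 1+ on dipstick, unless a 24-hour collection shows less than 1000 mg.

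**Section 7.1.**
- General table, tolerable and manageable Grade 2: "Continue cabozantinib treatment at the current dose level with supportive care". Grade 3 laboratory abnormalities without clinical relevance are left out of the interruption row. A footnote limits adjustment to toxicity that is related to the drug or of unclear cause.
- Proteinuria: "No change in cabozantinib treatment required if UPCR" is at most 2 mg/mg, or 24-hour protein is at most 2 g. At UPCR of 1 or below, neither treatment nor monitoring changes. If UPCR stays between 1 and 2 for a month, only the testing frequency changes.
- Liver: for drug-related Grade 2 values lasting over a week, a reduction is to be considered. A hold is specified from Grade 3.
- Pancreas: "Cabozantinib should be held if patient experiences Grade 3 asymptomatic amylase or lipase elevation".
- Blood counts: "If a patient experiences dose-limiting Grade 4 neutropenia or thrombocytopenia, the treatment will be withheld".

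**Dosing.** Section 4.2: "Drug cycles will last 28 days and be continuous for up to 12 months of therapy on study". The same section also holds drug for toxicity until it has fallen to Grade 1.

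**The concern.** Under continuous dosing there is no rest period between cycles, so refusing to start the next cycle means interrupting daily drug. The Study Schedule places the laboratory tests on Day 28, and the same result feeds both the cycle-start rule and Section 7.1. If the first says the cycle may not begin and the second says treatment continues unchanged, a treating physician cannot follow both. Section 7 also gives no delay limit, re-test rule or removal rule for a cycle that cannot start.

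Safety and tolerability is a primary aim in a trial of 11 patients. Interruptions, removals and cumulative exposure would then partly reflect which section was applied, as well as the drug.

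**Working it through.** The plan states no figure to reproduce here. The check sets the rules side by side and adds a small calculation for urine protein, the one analyte with numeric limits printed on both sides.

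**1. Urine protein, 24-hour route.** Eligibility is rescued by a 24-hour value below 1000 mg. The proteinuria table requires no change up to 2 g. From 1000 to 2000 mg the rescue is unavailable, so eligibility rests on the spot test. Concentration (mg/dL) = 24-hour protein (mg) / [urine volume (L) x 10]. The volume needed to stay at 30 mg/dL is protein / 300 litres. The documents give no urine volumes, so 0.5 to 2 L/day is my assumption.

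| 24-hour protein | Volume needed for 30 mg/dL | At 0.5 L/day | At 2 L/day |
|---|---|---|---|
| 1000 mg | 3.33 L | 200 mg/dL | 50 mg/dL |
| 1500 mg | 1500/300 = 5.00 L | 300 mg/dL | 75 mg/dL |
| 2000 mg | 6.67 L | 400 mg/dL | 100 mg/dL |

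Throughout the assumed range the urinalysis limit is exceeded, and a dipstick above 1+ is to be expected. With the spot test above limit, the cycle-start rule is not met while the proteinuria table asks for no change.

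**2. Urine protein, scheduled tests only.** Urinalysis and UPCR are both due on Day 28 of every cycle. Suppose the urinalysis or dipstick is above limit, UPCR is 1 mg/mg or less and no 24-hour collection is made. The cycle-start rule fails, and the first row of the proteinuria table changes nothing.

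**3. Persistence.** A month is at least as long as a 28-day cycle, so the table's provision for UPCR between 1 and 2 over a month must span a cycle start. Eligibility is not expressed as UPCR, so the conflict arises only if the spot test is above limit and no 24-hour value under 1000 mg rescues it.

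**4. Conflicts of principle.** The cycle-start rule has no grade, attribution or relevance condition. The general table has all three. A tolerable Grade 2 value, a clinically non-relevant Grade 3 value or an unrelated abnormality may continue there, yet any of them that lies outside an eligibility limit blocks the next cycle. The Grade 2 liver provision has the same structure.

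**5. Other analytes.** ALT: 110/45 = 2.44 x ULN. The matching Section 7.1 rules are written in CTCAE v5.0 grades, whose cut-offs the documents do not print. No numeric gap is therefore asserted for ALT, bilirubin, platelets, amylase or lipase.

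**6. ANC.** The exception is at least 1000/mm3 and eligibility is at least 1000/mm3. It relaxes nothing.

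**7. Frequency.** The schedule runs to Cycle 12, so the rule applies at up to 12 - 1 = 11 cycle starts per patient.

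**The case against.** The strongest defence is that the two rules work at different times: one decides whether a cycle may begin, the other manages events within a cycle. Moreover, the general table is headed as recommended guidance, and the proteinuria table says only that no change is required, so withholding the next cycle would breach neither. This has some force, but no section draws the distinction. With continuous dosing and a table that foresees a month of raised UPCR, the two rules meet at every cycle boundary.

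The restart rules for haematologic and non-haematologic toxicity do use eligibility (or, in places, baseline) values with a 14-day limit, which is consistent with the cycle-start rule. They cover dose-limiting toxicity, not a lesser abnormality found on Day 28.

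The 24-hour collection is only to be considered and is not a scheduled Day 28 test. That limits how often step 1 would arise, but step 2 does not need it.

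A reader might infer that Section 7.1 withholds drug only at Grade 4 for platelets and only at Grade 3 for amylase or lipase. The documents do not support that. The general table also provides for interruption at Grade 3, at Grade 4 and for intolerable Grade 2 events, and Section 4.2 adds its own hold for toxicity.

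Variation between sites is not at issue, since all patients enrol at one institution with weekly review of toxicities and dose adjustments. The inconsistency would be between readers or over time.

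**Conclusion.** The contradiction stands. It is firmest for urine protein, where the printed limits diverge for 24-hour values from 1000 to 2000 mg whenever the spot test is also above limit. That condition rests on the assumed urine volumes, but avoiding it would take 3.33 L a day or more. The conflict of principle with the general table and the Grade 2 liver provision needs no volume assumption and no grade cut-offs. The missing consequence when a cycle cannot start is a further gap. The ANC clause is a drafting fault with no effect on any decision.

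The size is qualitative: interruptions, exposure and tolerability are affected at up to 11 decision points per patient. A reader might go further and put a number on the patients managed differently, or count each as 1/11 = 9.1 points of the disease control rate. The documents support neither. They give no rate at which Day 28 values exceed eligibility limits, and the background frequencies of laboratory adverse events are not such a rate. Disease control is classified by RANO, so a delayed cycle does not itself reclassify a patient. The efficacy population excludes significant protocol violations, but the plan does not say that starting a cycle outside the limits would count as one.

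**What to change.** Reconcile Section 4.2, the cycle-start criteria in Section 7, and the Section 7.1 provisions (general table, haematologic, non-haematologic, proteinuria, liver and pancreatic). In Section 7:

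- state which rule governs at a cycle start when a value fails eligibility but Section 7.1 lets treatment continue;
- state what happens when a cycle cannot start, including re-testing, any maximum delay and when the patient leaves protocol therapy;
- correct the ANC exception or delete it.

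Which limit applies is a decision for the sponsor's clinicians, and no view is taken here. The cost is a short protocol amendment, with no extra tests, visits or patients.
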